Pre-Screening Phase – Patients interested in volunteering will be evaluated for eligibility by a research assistant. Candidate patients will be asked to provide their oral consent to participate in the screening questionnaires. This includes a yes-no questionnaire and multiple-choice questions by phone or in person.

After completing the screening procedures, eligible patients will provide informed consent.

During that visit, one of the research assistants will answer any further questions the candidate patient may have regarding the study. Patients will have 1 week to decide whether they would like to participate in the study.

Phase I – Initial Medical Assessment and Baseline Measurements

After obtaining informed consent, an initial medical assessment of the included subjects will be conducted by a licensed physician/neurosurgeon of our UW Neurological Surgery Department. Baseline upper extremity functional measurements and health-related questionnaires will be obtained by one of the research assistants/scientists at the UW Department of Rehabilitation Medicine and/or the Amplifying Movement & Performance Laboratory (AMP Lab). [name]. Initial medical assessment and outcome measurements include:

- A complete physical and neurological exam
- Graded and Redefined Assessment of Strength, Sensibility, and Prehension Test (GRASSP)
- International Standards for Neurological Classification of Spinal Cord Injury (ISNCSCI)
- Hand strength measurement by grip and pinch dynamometry
- WHO-Quality of life – BREF

After the initial assessment, patients will be scheduled for additional hand function measurements up to 2 times per week for up to 4 weeks (no more than four sessions total). These sessions measure the stability of the underlying disability and control for test-retest learning. Each session will last 1-2 hours. These recurrent measurements will include:

- GRASSP test Quantitative Prehension Subscale
- Vital signs (blood pressure, heart rate)
- Hand strength measurement by grip and pinch dynamometry

Phase II – Intervention Phase

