After Phase I, patients will be randomized to receive either physical therapy alone (Arm A) or physical therapy plus transcutaneous spinal cord stimulation (Arm B) for 6 weeks. Then, patients will be followed up for an 8-week wash-out period, during which neither study intervention will be administered. During wash-out period, patients will not be allowed to receive treatments that violate exclusion criteria (e.g., botulinum toxin injections or tendon/nerve transfer

surgery in the upper extremity) or new treatments that could affect the study's outcome (e.g., alternative exercise therapies or robotic rehabilitation targeting upper extremity function).

However, they can continue to get their regular lower extremity physiotherapy.

Next, the intervention arms will be crossed over, i.e., patients who received the A intervention arm first will receive the B intervention arm, and vice versa, for another 6 weeks. In each intervention arm, sessions will last 2 hours/day, 2-5 days/week.

Transcutaneous Spinal Cord Stimulation Procedure: Transcutaneous spinal electrical stimulation is a non-invasive neurostimulation technique. Stimulation will be delivered through the skin using surface hydrogel electrodes, which are commonly used in practice today.

During the first stimulation session, optimal electrode placement and stimulation parameters will be determined using hand function testing and electromyographic (EMG) testing of the upper extremity muscles. Hand function will be tested by the abbreviated GRASSP test, Quantitative Prehension subscale, pinch and grip force measurements, and Capabilities of Upper Extremity Test (Cue-T). EMG testing will be done using skin surface recording electrodes.

Transcutaneous spinal stimulation paradigms that elicit appropriate muscle activation with the lowest threshold stimulation current will be identified. A painless cutaneous enabling motor control paradigm will be used for this purpose: biphasic or monophasic rectangular pulses of 1.0 ms per phase duration will be delivered at a frequency of approximately 30 times per second (Hz). Within these pulses, a very high carrier frequency of 10 kHz is delivered to avoid painful sensations as the current crosses the skin (i.e., the Russian Method of muscle stimulation). Stimulation intensity will range from 1 to 180 mA. During the initial testing, stimulation will be delivered for a duration of 10 to 30 seconds.

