After determining the optimal initial stimulation configuration, we will deliver physical therapy sessions while transcutaneous spinal stimulation is administered for a total of up to 90 minutes. The duration of 90-minute stimulation is determined based on the effect mechanism and safety information reported in earlier clinical studies with spinal stimulation. Time without stimulation will be interspersed to examine the difference in movement with and without stimulation.

Hand and Arm Physical/Occupational Therapy Protocol: The therapy program will include progressive functional task practice for upper extremity motor training (i.e., active assistive range of motion, stretching, strengthening, reaching and grasping exercises, and fine motor skills training). The physical therapy program will be tailored to the patient's specific functional deficits and needs.

For safety monitoring, we will document vital signs (blood pressure, pulse, respirations, temperature), orientation to time and place, and skin examination before and at the end of each

session. For cardiovascular safety, non-invasive continuous blood pressure monitoring will be done during transcutaneous cervical spinal electrical stimulation. Patients will be encouraged to report any abnormal feelings and discomfort throughout the session. After each session, patients will be released if they are deemed stable. If not, they will be referred to a healthcare professional for evaluation and provided appropriate care.

Every two weeks throughout the intervention, we will measure and document the functional improvements observed during stimulation and those that persist beyond the stimulation. At the end of each intervention arm and wash-out period, outcome measurements will be repeated, as described in the study design figure above.

Phase III – Follow-up

After completing the two-arm crossover intervention phase (Phase II), patients will be provided with a home rehabilitation exercise program. Three follow-up visits during the early follow-up period (8 weeks following the last intervention session) and one last follow-up visit at the end of one year of the study will be scheduled, where assessments and measurements will be done as described in the study design figure above, at UW Rehabilitation Department and/or in Amplifying Movement & Performance Laboratory.

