Official Title of the study: ADDRESS: Activity Dependent Rehabilitation via Transcutaneous Electrical Spinal Stimulation to Restore Upper Extremity Functions in Spinal Cord Injury

NCT number: NCT03184792

Date of the document: February 22, 2022

Statistical Analysis Plan:

For comparison of the functional changes occurring during each intervention phase, one-way repeated measures ANOVA will be used with post-hoc pairwise analysis as per Tukey LSD test (IBM SPSS version 26). A Shapiro-Wilk Test will be used to determine whether repeated measurements follow a normal distribution. Mauchly's test will be used to analyze the assumption of sphericity, and degrees of freedom will be corrected using Greenhouse-Geisser estimates of sphericity when the assumption is violated. We will directly compare the benefits of training alone and stimulation combined with training by calculating the cumulative changes in each outcome measure across the two intervention arms. These values will be normalized to baseline to control for individual variation in function at the beginning of the study and compared between the training and stimulation + training interventions using a paired-samples T-test.

Additionally, score changes relative to the preceding treatment block will be calculated to compare the improvement rates between intervention phases repeated monthly. For all tests, $p < 0.05$ will be considered significant. All participants' data will be included in all analyses. Given the early stage of research and the lack of prior data on transcutaneous spinal cord stimulation for restoring upper limb function, power analysis and sample size calculations are not feasible.

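### The direct comparison normalises to a study-start value that both of a participant's arms share, so it cannot adjust the paired contrast, and the paired t-test ignores the order received

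*SAP*

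**What the plan says.** The first paragraph of the SAP sets out the direct comparison in three steps:

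- It begins by "calculating the cumulative changes in each outcome measure across the two intervention arms".
- It then scales the results: "These values will be normalized to baseline to control for individual variation in function at the beginning of the study".
- The scaled values are "compared between the training and stimulation + training interventions using a paired-samples T-test".

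The SAP does not say whether a change runs from the start of each arm or from the start of the study. It does not say whether normalising means subtracting or dividing. It names no covariate and no term for order or period. A further analysis is planned in which "score changes relative to the preceding treatment block will be calculated to compare the improvement rates between intervention phases". That is also a difference, not a covariate adjustment.

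The Protocol describes a randomised two-period crossover: "patients who received the A intervention arm first will receive the B intervention arm, and vice versa, for another 6 weeks". Between the arms, "patients will be followed up for an 8-week wash-out period". Both start-of-arm levels are collected. For the first arm, in Phase I, "Baseline upper extremity functional measurements and health-related questionnaires will be obtained". For the second arm, under Phase II, "At the end of each intervention arm and wash-out period, outcome measurements will be repeated".

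**The concern.** The stated aim of the normalisation is to remove differences between people in their initial function. A paired analysis already does that. What can still differ within a participant is the level at which each arm began and whether the arm came first or second. A single study-start value says nothing about either.

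Order matters because this is a rehabilitation trial with training in both periods. Gains in the first six weeks may well differ from gains in the second six weeks, whichever intervention is given. If they do, an analysis without order counts that systematic difference as random error. With unequal numbers in the two orders, it also shifts the estimate. At stake is the only direct test of what stimulation adds, in a trial whose SAP states that no power calculation was feasible.

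**Working it through.** The plan has no figure to reproduce: the documents state no sample size, power, SD, effect or correlation. The 0.05 level is from the SAP, and two-sided testing is assumed. Values of n and r below are assumptions.

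**1. The normalisation.** Let b be a participant's study-start value, Y an end-of-arm value and Δ an arm's change.

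- Subtracting, with change from study start: (Y_B − b) − (Y_A − b) = Y_B − Y_A. With change from arm start: (Δ_B − b) − (Δ_A − b) = Δ_B − Δ_A. In both cases b cancels.
- Dividing: Δ_B/b − Δ_A/b = (Δ_B − Δ_A)/b. For the same raw difference, a participant with half another's baseline counts twice as much. Nothing that differs between the two arms is adjusted for.

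**2. Order received.** Let D be the B-minus-A difference in change, with SD 1 within each order. Let τ be the true effect and π the second-period gain minus the first-period gain. Then D averages τ + π for those given A first and τ − π for those given B first.

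- With n1 given A first and n2 given B first, the overall mean is τ + π(n1 − n2)/n. It is unbiased only if the orders are balanced or π = 0.
- With balanced orders, the paired t-test's expected variance is 1 + π²n/(n − 1). At n = 10, π = 0.5 gives 1 + 0.25 × 10/9 = 1.28, so the standard error is about √1.28 = 1.13 times too large. For π = 1 it is 1 + 10/9 = 2.11, a factor of about 1.45.
- An order term removes π and moves the degrees of freedom from n − 1 = 9 to n − 2 = 8.

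Simulated power at n = 10, for an effect that gives about 50% power when π = 0:

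| π (SD of D) | no order term | order term |
|---|---|---|
| 0 | 0.50 | 0.49 |
| 0.5 | 0.41 | 0.50 |
| 1 | 0.20 | 0.49 |

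**3. The start-of-arm difference as covariate.** Let r be the correlation, across participants, between the B-minus-A difference in start values and that in end values, with equal variances assumed. Large-sample variances are 2(1 − r) for the arm-start change score, 1 for end values alone and 1 − r² with the covariate.

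- Against arm-start change scores, the ratio is (1 − r²)/[2(1 − r)] = (1 + r)/2: 0.65 at r = 0.3, 0.75 at 0.5, 0.85 at 0.7 and 0.95 at 0.9.
- If change runs from study start, the plan compares end values and the ratio is 1 − r²: 0.91, 0.75, 0.51 and 0.19. At r = 0 there is then no gain.
- Estimating the slope alongside order multiplies the variance by (n − 3)/(n − 4). Break-even against arm-start change scores is r = 2(n − 4)/(n − 3) − 1: 0.33 at n = 6, 0.71 at n = 10, 0.88 at n = 20 and 0.95 at n = 40.
- Mean 95% CI widths with order in both models, change score against covariate, in SDs of the end-value difference: n = 10, r = 0.3, 1.67 against 1.47; n = 10, r = 0.7, 1.09 against 1.10; n = 6, r = 0.5, 2.13 against 2.44; n = 20, r = 0.5, 0.93 against 0.83.

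**4. Plausible r.** With visits at weeks 0, 6, 14 and 20 of the crossover (6 + 8 + 6) and visit correlations ρ by lag, r = (2ρ6 − ρ8 − ρ20)/[2(1 − ρ14)]. Correlations of 0.85 at every lag give 0. Correlations of 0.92, 0.91, 0.88 and 0.86 at lags 6, 8, 14 and 20 give 0.07/0.24 = 0.29. Correlations of 0.95, 0.93, 0.86 and 0.80 give 0.17/0.28 = 0.61. At n = 10 without carryover, where the change score has 50% power, repeated simulations of the covariate model with order gave about 0.69–0.71, 0.59–0.62 and 0.49–0.53 at these three values. At n = 6 and r = 0.61, power was 0.40 against about 0.51 for the change score.

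**5. Carryover.** Suppose a fraction c of the first-arm effect persists unchanged through the second arm. The B-minus-A end difference then averages τ(1 − c/2) and the start difference −cτ/2. The change score returns τ. The covariate model with slope r returns τ[1 − c(1 − r)/2].

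- For c = 0.5 that is 0.75, 0.82 and 0.90 of the effect at r = 0, 0.29 and 0.61. Simulation agreed (about 76–89%), with power 0.42–0.46 against 0.50.
- For c = 1 it is 0.50, 0.65 and 0.81 (simulated 51%, 65% and 79%), with power 0.21, 0.26 and 0.32.

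**The case against.** A reader might infer that the plan certainly loses precision because it does not use start-of-arm values as a covariate, and that a covariate model should be primary. The documents do not support this. They give neither n nor r, and the covariate model is no better, or worse, at very small n or high r. If change is taken from each arm's start, those values already enter with a slope fixed at 1. The SAP's separate block-to-block changes show that later levels are not ignored.

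The case against the covariate model as primary is stronger still. The second arm's start value is measured after randomisation and after the first treatment. Lasting improvement is among the Protocol's primary objectives, so carryover is a condition the trial looks for. Under it the covariate model understates the effect, most severely at low r, where its promised gain over arm-start change scores is largest. Choosing a change score is therefore defensible. In addition, Phase I allows up to four further sessions of prehension and strength measurement, and averaging these could reduce noise in the first start value for those outcomes without any covariate.

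All of this stands. It does not rescue the study-start normalisation, which fails to adjust the contrast under either reading, and it does not justify omitting order received.

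**Conclusion.** The point holds in two parts. First, the normalisation cannot adjust the within-participant comparison; this is algebra and needs no assumption about n or r. Second, the paired t-test ignores order. At n = 10 with balanced orders, that costs about 0.09 in power if period gains differ by 0.5 SD and about 0.29 if they differ by 1 SD, against a price of about 0.01 for including the term when they do not differ. The documents do not show that a period difference of this size will occur.

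That a start-of-arm covariate would improve precision is conditional on n, r and the reference point for change, and it is offset by understatement of the effect if first-arm gains persist. It supports a sensitivity analysis, not a change of primary estimator.

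**What to change.** In the SAP's direct comparison:

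1. Remove the normalisation to study start.
2. Define each arm's change as its end value minus that arm's own start value: Phase I for the first arm, end of wash-out for the second. Where Phase I measures are repeated, say which value, or what average, is used.
3. For each outcome, analyse the B-minus-A difference in change with a term for order received, the orders weighted equally, and report the estimate with its 95% CI.
4. Prespecify, as a sensitivity analysis, a regression of the end-of-arm difference on the start-of-arm difference plus order. State that it may be more precise but understates the effect if first-arm gains persist through the second arm.

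The cost is SAP wording, one degree of freedom for order in the main analysis and a little more analysis work. No new visit or measurement is needed.

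### The direct treatment comparison in this randomised two-period crossover has no period term; adding one is a cheap improvement in precision and in protection against conditional bias

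*SAP*

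**What the plan says.** Under Phase II – Intervention Phase, the protocol randomises patients to start with physical therapy alone (A) or with therapy plus stimulation (B) for 6 weeks. There follows an "8-week wash-out period, during which neither study intervention will be administered". The arms then cross over: "patients who received the A intervention arm first will receive the B intervention arm, and vice versa, for another 6 weeks". This is an AB/BA design.

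The Statistical Analysis Plan makes its direct comparison on cumulative changes in each outcome, normalised to baseline and "compared between the training and stimulation + training interventions using a paired-samples T-test". The other named model is a one-way repeated measures ANOVA. Neither analysis is given a period or sequence term. The SAP does not say from which measurement the second period's change is counted. It gives no sample size and says that none could be calculated.

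Three further provisions bear on the point. Phase I includes repeated hand function tests before randomisation: "These sessions measure the stability of the underlying disability and control for test-retest learning". During treatment there is more testing: "Every two weeks throughout the intervention, we will measure and document the functional improvements observed during stimulation". And "At the end of each intervention arm and wash-out period, outcome measurements will be repeated", so a second-period starting value is already collected.

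**The concern.** In a patient who receives A then B, the difference B − A contains the treatment effect plus any difference between period 2 and period 1. In a patient who receives B then A, it contains the treatment effect minus that difference. The paired t-test treats the two kinds of patient as one sample, so a period effect acts as extra spread when the sequences are equal in size, and partly as bias when they are not.

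A period effect here means only that changes differ between periods, for example through practice, drift or less room to improve. If each change is counted from its own period's start, a stable gain kept from period 1 drops out. The protocol treats test-retest learning as something to be controlled. Patients who complete period 1 also enter period 2 after a good deal of training and testing: "In each intervention arm, sessions will last 2 hours/day, 2-5 days/week" over 6 weeks is 6 × 2 × 2 = 24 to 6 × 5 × 2 = 60 hours.

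At stake are the width of the interval, the power of a trial that may be small, and the accuracy of the estimate for the one split of sequences that actually occurs.

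**Working it through.** **Inputs.** From the documents: AB/BA design, paired t-test, p < 0.05 (two-sided assumed). Assumed, because the documents give none: n, the split between sequences, the period effect and the treatment effect. The unit is the within-patient SD of B − A (SD = 1). The treatment effect is τ = 1 for power and 0 for type I error. The changes are read as counted from each period's own start. The plan states no figure to reproduce.

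**Model.** d = τ + π in AB patients and τ − π in BA patients, plus error with SD 1, where π is the period-2 minus period-1 change.

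**Paired t-test.**
- Expected estimate: τ + π(nAB − nBA)/n.
- True variance given the split: 1/n.
- Expected estimated variance: [1 + 4·nAB·nBA·π²/(n(n − 1))]/n.

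**Period-adjusted estimate.** Half the between-sequence difference in period differences, which equals the average of the two sequence means of d. It is unbiased for τ, with SE ½√(1/nAB + 1/nBA) and n − 2 df.

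**Equal sequences, n=12 (6:6).** At π = 0.5 the expected estimated variance is [1 + 4·6·6·0.25/(12·11)]/12 = 1.273/12 = 0.106, against a true variance of 1/12 = 0.083. Power and type I error come from the exact distributions; mean SE and coverage come from simulation.

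| π (SD) | True SD of estimate | Mean estimated SE | 95% CI coverage | Paired power | Adjusted power | Paired type I error |
|---|---|---|---|---|---|---|
| 0 | 0.29 | 0.28 | 95% | 88% | 88% | 5.0% |
| 0.25 | 0.29 | 0.29 | 96% | 87% | 88% | 4.4% |
| 0.5 | 0.29 | 0.32 | 97% | 82% | 88% | 3.0% |
| 1 | 0.29 | 0.41 | 99% | 61% | 88% | 0.6% |

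**Unequal sequences, n=12 (8:4).** Absolute bias is π × 4/12, that is 0.08, 0.17 and 0.33 SD at π = 0.25, 0.5 and 1. Paired power is 92%, 93%, 92% if the bias is upward and 81%, 67%, 26% if downward, against 84% adjusted. Paired type I error is 5.1–5.5%. The adjusted SE is ½√(1/8 + 1/4) = 0.306, against 0.289 unadjusted.

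**Type I error for other splits** at the same three period effects: 11:5 (n=16) gives 5.8%, 7.5%, 10.1%; 7:5 (n=12) is conservative at 1.5–4.6%. Averaged over simple randomisation at n=10 to 20 it is 5.0–5.2%.

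**Cost of adjusting when π = 0 (τ = 1), and the period effect above which adjusting gains power.** Simple randomisation is averaged over the binomial splits; an empty sequence counts as no rejection for the adjusted test.

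| n | Paired power | Adjusted, equal split | Adjusted, simple randomisation | Break-even π, equal | Break-even π, simple |
|---|---|---|---|---|---|
| 6 | 51% | 46% | 40% | 0.32 | 0.59 |
| 8 | 68% | 66% | 59% | 0.24 | 0.47 |
| 10 | 80% | 79% | 74% | 0.20 | 0.41 |
| 12 | 88.3% | 87.6% | 84% | 0.17 | 0.37 |

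**Form of the adjusted model.** A random-patient model whose patient variance cannot go below zero gives the same estimate as the two-sample form, but a smaller SE when that variance is estimated as zero. By simulation at n=12 (6:6), with assumed between-period correlations of 0.5, 0.2, 0 and −0.2:
- Zero-variance fits: 5%, 27%, 50%, 73% of trials.
- Type I error with pooled df at the boundary: 5.0%, 5.5%, 6.3%, 7.8%.
- Type I error with n − 2 df: 5.0%, 5.3%, 5.7%, 6.7%.
- Two-sample form: about 5% throughout.

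Low or negative correlation is possible because the outcome is a change score.

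**The case against.** No period effect is shown, and the documents give no size for one. The Phase I pre-tests and the 8-week wash-out are there to reduce it. The hours of training before period 2 are weak evidence, since a stable retained gain cancels from own-start changes, and the 1 SD scenario is as large as the whole assumed treatment effect. All this stands. It limits how much can be claimed, but the planned analysis would neither reveal a period effect nor remove one.

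The planned test also protects against false positives. With equal sequences it is conservative. A reader might infer from the 11:5 figures that the trial runs an inflated type I error. The documents do not support that: under simple randomisation a split at least that unequal at n=16 has probability 21%, and the average over all splits is near 5%. Nor can one infer that balancing was omitted. The text states no method, but the design figure is not shown, so no omission is claimed. Even with balanced allocation, drop-out or an odd n can leave the sequences unequal.

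Finally, at very small n the adjustment costs noticeable power, and the SAP describes early-stage research with no stated n. That stands and belongs in the decision.

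**Conclusion.** The point holds as one about precision and conditional bias. The randomised order is a known design feature that the direct comparison ignores. If changes differ between periods, equal sequences give an unbiased estimate with too wide an interval, and unequal sequences give an estimate shifted by π(nAB − nBA)/n in either direction. It does not make the paired test invalid, and overall false-positive control is intact.

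The algebra is firm. The practical size is unknown, because n, SD, period effect and split are all assumed. The conclusion also rests on reading the cumulative changes as within-arm changes from each period's start, which the SAP does not settle. Below the break-even period effect the paired test has more power. Minor to moderate improvement.

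**What to change.** Amend the SAP's direct comparison as follows.

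1. Keep the baseline-normalised change, and state that each change is counted from its own period's start: end of Phase I for period 1, and end of the first wash-out for period 2.
2. Replace the paired t-test with half the between-sequence difference in period differences, tested by a two-sample t-test on n − 2 df. A linear model with treatment, period and fixed patient effects gives the same analysis.
3. Do not treat a random-patient model with non-negative patient variance as equivalent, for the reason shown in the working.
4. Report the paired t-test as supportive if wanted. The ANOVA and the preceding-block changes can stay as planned.
5. State that the period term does not correct unequal carryover. If an effect r is retained after B only and a fraction f of it is left at the end of period 2, the adjusted estimate shifts by (1 − f)r/2. With r = 0.5 SD and a true effect of 1, it is 1.00 if the retained effect is stable, 1.125 if half fades and 1.25 if all fades.

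The cost is a few sentences of SAP text, one degree of freedom and some precision when sequences are unequal. No extra patients, visits or measurements are needed. The sponsor should weigh the power loss in the cost table against the expected n before adopting the change.

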Recently, a non-invasive technique for spinal stimulation, specifically transcutaneous electrical spinal cord stimulation, has been demonstrated to be effective in improving motor function in both healthy individuals and patients with spinal cord injuries. The effects of this novel technology on upper extremity motor function have not been tested. This research study employs a prospective, experimental, randomized crossover design to assess the safety and efficacy of transcutaneous cervical electrical stimulation in improving upper limb function in patients with cervical spinal cord injury.

Electrical cervical stimulation has been shown to be effective in improving upper limb function in animal studies conducted in our laboratory. By other groups, transcutaneous electrical spinal

cord stimulation has been demonstrated to be effective in improving lower extremity motor function in both healthy individuals and patients with spinal cord injury. Transcutaneous spinal stimulation was applied to the skin via external electrodes placed midline on the spinous processes of the vertebrae. A novel, well-tolerated, and painless transcutaneous electrical enabling motor control strategy was used for neuromodulation. Previously, no adverse effects have been reported with transcutaneous electrical spinal cord stimulation. Patients described a non-disturbing tingling sensation beneath the electrodes.

The purpose of the study is to implement and test transcutaneous spinal stimulation in patients with cervical spinal cord injury (traumatic or degenerative etiology) in combination with a rehabilitation program. We aim to enhance both arm and hand sensorimotor functions.

Our primary objectives are:

1. To establish a novel, non-invasive therapeutic stimulation approach in patients with cervical spinal cord injury.
2. To determine transcutaneous stimulation locations and parameters that are safe and effective for augmenting hand motor and sensory function.
3. To evaluate both immediate and lasting improvements in hand motor and sensory function via transcutaneous cervical spinal stimulation.

Our secondary objectives are to document and analyze other potential benefits of electrical neuromodulation, including a decrease in spasticity, an increase in bowel and bladder control, and an improvement in mobility.

Inclusion Criteria. Individuals who

1. has cervical (C7 or higher) spinal cord injury with a duration of at least 1 year duration

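### The SAP tests stimulation + training against training on every outcome at p < 0.05, with no primary outcome, adjustment across outcomes or exploratory label

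*SAP*

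**What the plan says.** The direct test of stimulation is in the first paragraph of the SAP. It is made by "calculating the cumulative changes in each outcome measure across the two intervention arms". Of the resulting values the SAP says "These values will be normalized to baseline to control for individual variation in function at the beginning of the study", and they are then "compared between the training and stimulation + training interventions using a paired-samples T-test". No formula for the normalization is given.

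Two other sets of comparisons stand beside it. Within each intervention phase, "one-way repeated measures ANOVA will be used with post-hoc pairwise analysis as per Tukey LSD test". In addition, "score changes relative to the preceding treatment block will be calculated to compare the improvement rates between intervention phases". One threshold covers all of them: "For all tests, $p < 0.05$ will be considered significant".

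The protocol describes the design as one "to assess the safety and efficacy of transcutaneous cervical electrical stimulation in improving upper limb function". It lists three primary objectives. The nearest to an efficacy endpoint is the third, on immediate and lasting gains in hand function, and it names no instrument, time point or contrast. Phase I lists the GRASSP, ISNCSCI, grip and pinch dynamometry and the WHO quality-of-life questionnaire, and ranks none of them. Phase II refers to the study design figure for the measurement schedule, and that figure is not available here.

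**The concern.** When every outcome is tested at 0.05 and none is designated in advance, the error rate for the statement that stimulation improved function is not 5%. It is the chance that at least one of several tests succeeds, and that grows with their number. The plan gives no basis for deciding which result carries the efficacy conclusion, so the choice can be made after the results are seen. The practical risk is selective emphasis: one favourable measure is presented as the finding and the others recede.

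The post-hoc procedure in the SAP does not help. Under either reading of its name, it acts on pairwise comparisons within the ANOVA of one outcome. It does not reach the paired t-tests across outcomes.

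**Working it through.** **Plan's own figure.** The only error rate stated is 0.05 per test. There is no family-wise level, sample size or power to reproduce.

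**Inputs.**
- Per-test level: 0.05 (SAP). Sidedness is not stated; two-sided is assumed.
- Number of outcomes, m (assumed): 5 if the Phase I instruments count as GRASSP, ISNCSCI, grip, pinch and WHO quality of life. It is 7 if the three GRASSP domains are tested separately (3 + 4). Ten is shown as a further case in which more subscales are tested.
- The CUE-T is left out because the protocol names it only for choosing electrode placement and stimulation parameters.
- Patients, n (assumed): 10 and 20. Correlation between the outcomes' paired differences (assumed): 0 to 0.8.

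**Independent outcomes.** The chance of at least one p < 0.05 with no true effect is 1 − 0.95^m:
- m = 5: 1 − 0.95^5 = 0.226
- m = 7: 1 − 0.95^7 = 0.302
- m = 10: 1 − 0.95^10 = 0.401

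**Correlated outcomes.** Paired t-tests were simulated under the null with equally correlated normal differences, at n = 10 and n = 20:

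| Outcomes | Correlation | n = 10 | n = 20 |
|---|---|---|---|
| 5 | 0.5 | 0.190 | 0.188 |
| 5 | 0.7 | 0.159 | 0.154 |
| 5 | 0.8 | 0.137 | 0.133 |
| 7 | 0.5 | 0.242 | 0.235 |
| 7 | 0.7 | 0.191 | 0.184 |
| 10 | 0.5 | 0.308 | 0.297 |
| 10 | 0.8 | 0.190 | 0.181 |

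For 5 to 7 outcomes at correlation 0.5-0.8 the range is therefore 13% (5 outcomes, 0.8) to 24% (7 outcomes, 0.5). If the CUE-T is also an outcome, 6 outcomes give 17-22% and 8 give 20-26% at correlation 0.5-0.7. These figures cover only the stimulation-versus-training t-tests. The ANOVA post-hoc tests and the improvement-rate comparisons come on top. With one primary comparison, the error for the primary claim is 5%.

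**Power cost of a Holm adjustment.** The strictest Holm step tests at 0.05 divided by the number of tests. Power is from the noncentral t with noncentrality 0.8 × √n (2.53 for n = 10, 3.58 for n = 20), for an assumed paired effect of 0.8 SD. Removing the primary from 5-7 outcomes leaves 4-6 secondary tests. One improvement-rate test per outcome adds 5-7, so the family becomes 4 + 5 = 9 to 6 + 7 = 13.

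| Tests in family | Level | n = 10 | n = 20 |
|---|---|---|---|
| 1 (unadjusted) | 0.05 | 62% | 92% |
| 4 | 0.0125 | 35% | 78% |
| 6 | 0.0083 | 28% | 73% |
| 9 | 0.0056 | 23% | 67% |
| 13 | 0.0038 | 18% | 62% |

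**The case against.** The best defence is that this is visibly early work. Two of the three primary objectives, establishing the approach and finding stimulation sites and settings, are developmental. The SAP gives no sample size, and nothing in either document promises a confirmatory claim. This has force, and it is why an exploratory declaration is accepted below as a complete remedy. But the SAP's sentence beginning "Given the early stage of research and the lack of prior data on transcutaneous spinal cord stimulation for restoring upper limb function" serves only to explain the missing power calculation. It does not qualify the significance rule, and the protocol's stated aim includes efficacy.

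A second defence is that a reader who sees every outcome can make the adjustment unaided. That is true if all are reported. The difficulty is that nothing in the plan fixes which result is the main one.

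Three stronger readings are tempting, and the documents do not support them.
- *That the protocol certainly has no primary endpoint.* The SAP text has none. The unseen figure is described as a design and measurement schedule, so a primary label there is unlikely, but it cannot be ruled out.
- *That a particular false-positive rate has been shown.* The number of outcomes, n and the correlation are not in the documents, so only a range under stated assumptions is possible.
- *That the post-hoc test seriously inflates error.* The name mixes Tukey's HSD, which controls family-wise error, with LSD, which does not adjust. Used after a significant F, LSD gives about 5% or less with 3 levels. With 4 levels it gives 6-13% if one level is shifted by 0.5 to 3 SD, but only 4-5% if the means rise to a plateau. The SAP does not state the levels or say that a significant F is required first, so this remains a minor point.

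**Conclusion.** The concern holds for the SAP as written: an unranked set of paired t-tests, each called significant at 0.05, with no adjustment across outcomes and no exploratory label. Under the stated assumptions the chance of at least one false-positive stimulation result is roughly three to five times the nominal 5% for 5 to 7 correlated outcomes (13-24%). The independent-outcome figures of 23-30%, and 40% for 10 outcomes, are upper bounds, since the hand measures overlap. Certainty is high for the SAP text and lower for the protocol, because of the missing figure. The data and the paired comparison remain usable; what cannot be interpreted without a further statement is an efficacy claim drawn from them. It should be fixed.

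**What to change.** Amend the SAP before outcome data are compared.

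1. Name one primary outcome, chosen by the sponsor with its reason. GRASSP Quantitative Prehension, grip and pinch are the most frequently measured candidates (Timeline for outcome measurements). Name one primary contrast: change over the stimulation + training block minus change over the training block, at the end of each 6-week block, by two-sided paired t-test at 0.05. State whether that assessment is made with stimulation on or off, since Phase II records gains both during stimulation and persisting after it. State also which baseline is used and the normalization formula. Without these, several versions of the single primary remain open.
2. Report all other outcomes and the improvement-rate comparisons with confidence intervals, either labelled exploratory or Holm-adjusted, and say which tests form the Holm family.
3. Alternatively, if the sponsor regards the whole trial as exploratory, or outcome data have already been compared, say so for all tests and make no confirmatory efficacy claim.

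Minor: replace the hybrid post-hoc name with Holm-adjusted paired t-tests, which do not need sphericity, and state the ANOVA levels compared.

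Cost: SAP wording only, with no new visits or data. On the Holm route, some results that would pass at an unadjusted 0.05 will no longer be called significant. The power table above gives the loss, which is larger if the improvement-rate tests join the family. The exploratory label avoids it.
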